21.4 Costing

[figure not shown]
Costs will be estimated as the sum of the product of resources (e.g. staff minutes) times unit costs (e.g. compensation levels). “Economic” costs (the true value of resources consumed or “opportunity costs”) will be assessed by identifying the value of subsidized or donated resources with information from databases (e.g. wage rates) and donors. We will use prices prevailing at the time of study onset and will convert any locally incurred costs using the Uganda/Kenya Shilling / US dollar exchange rate at that time. Costs of CAB-LA implementation will be compared to the costs of oral PrEP implementation estimated during the primary trial to estimate the incremental cost of CAB-LA implementation.

21.5 Power and Sample size considerations

For each ongoing trial, we assume 90% of participants consent to the extension (reflecting the high retention in the ongoing trials seen to date). Of those, we assume 90% are retained through the extension. In the individually randomized ANC and OPD trials, we anticipate >80% power to detect a 11% or greater absolute increase in prevention coverage between arms with 162 participants/arm (assuming $\sigma = 0.35$). In the cluster-randomized community-based trial, we anticipate >80% power to detect a 15% or greater absolute increase in prevention coverage between arms with ~20 participants in each of the 16 clusters (assuming mean prevention coverage in the standard of care arm of 10%, $\sigma = 0.35$, and a matched-pair coefficient of variation $km=0.25$). These calculations are expected to be conservative given the ongoing enrollment and primary approach to conduct a pooled analysis as well as the increased precision from stratified randomization and through covariate adjustment with TMLE. Minimum

detectable effect sizes varying these assumptions (including allowing for lower retention in either the ongoing or extension studies) are shown in Figure 4.

Figure 4. Minimum detectable effect sizes for the primary hypothesis

22. DATA HANDLING AND RECORD KEEPING

This is an implementation study; the primary risks for a client would be any loss of confidentiality, or risk from blood draw in measurement of the HIV outcome. For risk mitigation, all participants undergo informed consent in their native language, staff are fully trained on confidentiality. The SEARCH Sapphire team has SOPs and procedures for data collection and security. Because CAB-LA is not yet approved in Uganda or Kenya, we will be recording Grade 3 and 4 AEs and reporting to these as required to regulatory authorities.

22.1 . Data Management Responsibilities

Data management for this study will be overseen by the Infectious Diseases Research Collaboration (IDRC) Data Management Center located in the main IDRC research complex in Nakasero, Kampala, Uganda. The Data Management Center (DMC) is also responsible for providing IT support to all staff members.

Data Management System

For any study components using paper data collection, IDRC has designed and developed a custom Data Management System that is used to manage the data, using Microsoft SQL Server as the backend for all data storage. MS Access is used for double data entry and SAS programs are used for comparing 1st and 2nd entry and generating discrepancy reports. In addition, the DMC has developed custom Visual Basic programming for direct survey and data entry of data in the field. Data Transformation Services/ SQL Server Integration Services (DTS/SSIS) packages are used to automatically import/export any new data and stored procedures written in T-SQL are used to automatically generate new data queries on a daily basis. There is a web

interface to the whole system written in ASP.NET to allow users to view the data, view reports, and even modify the data they are authorized to access. With regular backups and a full audit trail, the whole system is regulatory compliant (21 CFR Part 11).

22.2. Essential/Source Documents and Access to Source Data/Documents

Data is collected as a mixture of paper Case Report Forms (CRFs) and logs and electronic data capture from health facility databases and field data tablets. Data is entered locally and uploaded to the DMC after quality assurance measures have taken place. Only study investigators and staff affiliated with the study will have access to source data.

External data sharing will be made through a data request proposal procedure coordinated by the PIs and the IDRC Data Department. A standardized data request sheet will be completed by outside investigators and reviewed by the senior management and/or the Principal Investigator. Data and associated documentation will be available to users under a data-sharing agreement that provides for: (1) a commitment to using the data only for research purposes and not to identify any individual participant; (2) a commitment to securing the data using appropriate computer technology; and (3) a commitment to destroying or returning the data after analyses are completed. User registration is required to access or download files. As part of the registration process, users must agree to the conditions of use governing access to the public release data, including restrictions against attempting to identify study participants, destruction of the data after analyses are completed, reporting responsibilities, restrictions on redistribution of the data to third parties, and proper acknowledgement of the data resource.

22.3. Quality Control and Quality Assurance

The data management system is designed to collect, transfer and store data for Data Management Center studies. Data from any paper records will be 100% double entered into the system via Microsoft Access Databases or Web-based data entry screens. Locally collected data is compressed, password-protected, and then securely uploaded to a cloud based server (Network Solutions, Inc.) using secure-FTP via the FileZilla application. Cloud-based uploads are downloaded daily to the Kampala DMC. After the data has been input into the Data Management Center server, it is electronically verified and is then written to the SQL database. Edit checks or queries are run nightly and the results are posted to a secure clinical trials website so that the sites can electronically address problems with the data the next day. The site corrects data via the website and the database is updated automatically.

In order to ensure data security and integrity, the following measures will be implemented:

- All members of the study team will be educated in the study protocol prior to the onset of the study.
- Detailed Standard Operating Procedures (SOPs) will be written for all project activities and be provided to relevant team members.
- Team members will be thoroughly trained on the SOP's.
- Where applicable, team members will receive additional training on the use of tablet computers.
- All data transcribed from paper will be double data entered or verified.

- All electronic data will be backed up regularly.
- All data will be transferred to the main Data Center in Kampala to the secure server. This sever is backed up on a daily basis and a monthly backup is stored off-site.
- All computers, including the tablets, will be password protected.
- All computers, including tablets, will be locked in a secure room each night.
- Any Log Books and CRF's will be locked in a secure room each night.

23. PUBLICATION POLICY

The findings from this study may be published in a medical journal. No individual identities will be used in any reports or publications resulting from the study. The researchers will publish results of the study in accordance with NIH, UCSF, UNCST, KEMRI, and Makerere University guidelines.

1. OVERVIEW OF THE SEARCH CAB-LA EXTENSION STUDY

This study is testing the hypothesis that a “Dynamic Choice HIV Prevention” intervention that offers participants CAB-LA, oral Pre-Exposure Prophylaxis (PrEP), or post-exposure prophylaxis (PEP) and the ability to switch between products over time using a patient-centered delivery approach will achieve higher prevention coverage for males and females ≥ 15 years of age and at risk for HIV infection acquisition, as compared to the country standard-of-care (SoC). The current SoC for biomedical HIV prevention includes oral PrEP and PEP. This study is being conducted in rural western Uganda and rural western Kenya. The follow-up is over 48 weeks. Additional details of the study design, arms, and procedures can be found in the Study Protocol.

[figure not shown]
The primary objective is to evaluate the effect of the Dynamic Choice HIV Prevention intervention versus the SoC on biomedical HIV prevention coverage, defined as the proportion of follow-up time covered by either PrEP (oral PrEP or CAB-LA) or PEP. Secondary, pre-specified endpoints compared between arms and included in this SAP are coverage during periods of self-reported risk of HIV acquisition (“at-risk coverage”) and HIV incidence. We additionally describe product use over time between arms. Analysis plans for other endpoints (e.g., implementation metrics and the change in endpoints before and after adding CAB-LA to the intervention) are available elsewhere. Power calculations and history of changes are given in the Appendix.

2. POPULATION AND CHARACTERISTICS

The study population is persons who were enrolled in the 3 randomized Dynamic Choice HIV Prevention trials that recruited from antenatal clinics, outpatient departments, and the community.¹⁻³ These trials were designed to evaluate the impact of the Dynamic Choice HIV Prevention intervention (offering choice between oral PrEP and

PEP as biomedical HIV prevention options) versus the SoC on biomedical HIV prevention coverage over 48 weeks (Figure 1).

Figure 1: Schematic of the CAB-LA extension study with abbreviations of DCP for Dynamic Choice HIV Prevention intervention and SOC for standard-of-care.

The Dynamic Choice HIV Prevention trials enrolled participants aged ≥ 15 years with current or anticipated risk to acquire HIV. Inclusion criteria for the CAB-LA extension study are 1) Prior enrollment in a SEARCH Dynamic Choice HIV Prevention trial, 2) HIV-negative by country-standard rapid HIV testing algorithm, and 3) Residence in the study region. In the extension, participants maintained their original randomization arm and are not blinded to the treatment arm. The primary statistician ([name]) will remain blinded to the treatment arm until the official unblinding of the study when the primary and secondary effect analyses, described in this SAP, are conducted. Additional details, including randomization procedures and eligibility for CAB-LA access among intervention arm participants, are in the Study Protocol.

To characterize participant flow from original randomization through measurement of the primary endpoint of the extension, we will provide a CONSORT diagram. To describe the study population, we will summarize participant characteristics at start of the extension, overall and by arm. These characteristics will include recruitment setting, country, sex, age, marital status, occupation, pregnancy (women only), circumcision (men only), and alcohol use (having 1+ alcoholic drink per week).

3. ENDPOINT DEFINITION AND MEASUREMENT

3.1. Biomedical HIV Prevention Coverage

The primary endpoint of this study is biomedical HIV prevention coverage, defined as the proportion of follow-up time covered by either PrEP (TDF/3TC or CAB-LA) or PEP. Thereby, this endpoint has a minimum of 0% (no use) and a maximum of 100% (full coverage). For oral PrEP and PEP, coverage is defined using self-report via a structured survey administered at 24 and 48 weeks of follow-up. Specifically, for each month of the prior 6 months, participants retrospectively report any use of oral PrEP (i.e., pill ingestion) and any use of PEP. For CAB-LA, coverage is defined through injection logs. Coverage from CAB-LA begins 3 days after an injection and continues for 67 days.

3.2 At-Risk Coverage

A secondary endpoint of this study is at-risk coverage, defined as the proportion of follow-up time that a participant reports being at risk of HIV acquisition during which they are covered by a biomedical prevention option. Product use over time will be defined analogously to the primary outcome. Self-reported risk of HIV acquisition will be assessed retrospectively via the structured survey administered at 24 and 48 weeks of follow-up.

3.3 Incident HIV Acquisition

A secondary endpoint of this study is incident HIV acquisition. HIV rapid antibody testing and HIV RNA testing (Cepheid GeneXpert Diagnostic System, Sunnyvale, California) will be performed at baseline, week-24, and week48. HIV testing is also available at the Ministry of Health clinics at all study sites. All participants with detectable HIV RNA and negative rapid antibody testing will have repeat antibody testing for confirmation of HIV diagnosis. All possible incident HIV infections will be reviewed by two HIV clinical experts blinded to the trial arm to determine if the participant meets the definition of confirmed incident HIV infection.

4. EVALUATION OF THE EFFECT OF THE SEARCH DYNAMIC CHOICE HIV PREVENTION INTERVENTION WITH CAB-LA

4.1. Primary Analysis: Effect on Biomedical HIV Prevention Coverage

The primary endpoint of biomedical HIV prevention coverage will be compared between arms with targeted minimum loss-based estimation (TMLE) to improve efficiency over the unadjusted effect estimator.⁴⁻¹² Briefly, TMLE combines estimates of the outcome regression (i.e., the conditional expectation of the outcome, given the intervention and

covariates) and the known propensity score (i.e., the conditional probability of the intervention, given the covariates) to obtain doubly-robust inference for the estimand of interest.

The primary analysis will adjust for recruitment setting (antenatal clinic, outpatient department, or community) in the outcome regression and adaptively adjust for additional baseline covariates to optimize precision, while preserving Type-I error control. Specifically, we will use Adaptive Pre-specification to select the candidate TMLE that maximizes empirical efficiency.^{8,10,12} Using 10-fold cross-validation, we will select from the following prespecified candidates:

Outcome regression estimators: generalized linear models (GLMs) adjusting for a single covariate (beyond setting), main terms GLM, LASSO, or no further adjustment.

Propensity score estimators: GLMs adjusting for a single covariate, main terms GLM, LASSO, or no adjustment

Candidate variables: sex, age, alcohol use, mobility, or nothing

The primary analysis will estimate the marginal effect on the absolute scale (i.e., the difference in the average of the arm-specific outcomes). Secondary comparisons will be on the ratio scale. Standard error estimation will be based on the estimated influence curve, accounting for clustering from the community-based setting.^{9,10,13-15} Statistical inference will follow from the Central Limit Theorem.⁴ Specifically, we will create Wald-type 95% confidence intervals and test the null hypothesis of no difference in biomedical HIV prevention coverage with a two-sided test at the 5% significance level. We will also report point estimates and 95% confidence intervals for the arm-specific estimates.

In sensitivity analyses, we will assess the robustness of our findings by only adjusting for setting in the outcome regression as well as implementing the unadjusted effect estimator. We may conduct an additional sensitivity analysis adjusting for, instead of excluding, participants with zero follow-up. Additionally, we will evaluate the effect on coverage when restricting follow-up time to periods included in the structured survey administered to assess use of oral PrEP or PEP. In additional sensitivity analyses, we will use data from the initial trials through the extension and apply TMLE to adjust for differences between participants who did vs. did not continue in the extension and participants who did vs. did not have their endpoint ascertained. See Section 6 for details.

We will repeat these analyses within subgroups defined by sex and age group (15-24 years vs. 25+ years) and apply the Bonferroni correction for multiple testing. To further understand effect heterogeneity, we may conduct variable importance measures (i.e., unadjusted and adjusted predictor analyses) with TMLE.

Prior to locking this SAP, we will conduct treatment-blind simulations to verify Type-I error control for all endpoints.¹²

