This extension describes a 48-week extension of 3 ongoing randomized trials in SEARCH Phase A studying a patient-centered “Dynamic Choice Prevention” (DCP) implementation strategy for delivering existing evidence-based biomedical prevention interventions vs. standard of care (SOC). The Dynamic prevention model offers participants choices on prevention modality on an ongoing basis: oral PrEP, or oral PEP, and the option to switch between products. The trials are being conducted in 3 settings: antenatal (ANC) clinics, the outpatient department (primary care clinics), and in rural community settings in Western Uganda and Kenya. All clinic and village health team staff (i.e., Clinical Officers, nurses, coordinators, health workers) are trained and equipped for HIV prevention care in the clinical setting, appropriate to their role.

In this extension study, participants in the intervention and control arms are reconsented and remain in their initial randomized arm. Persons in the intervention arms who remain HIV negative will be offered CAB-LA as an additional biomedical prevention option, if eligible. CAB-LA will be delivered at health clinics. The primary 48-week endpoint for this extension is proportion of time covered by a biomedical prevention product. As of May 9, 2022, a total of 1213 HIV-negative persons aged 15 years and older and at risk for HIV acquisition were enrolled in the studies. (Table 1). New participants are currently being enrolled in the original SEARCH SAPPHIRE DCP trials to replace those participants who have moved or have been unable to continue in the DCP study. The total number of participants in the study eligible for CAB-LA will not exceed the 593 listed in Table 1.

Table 1. Enrollment in 3 SEARCH Sapphire Dynamic Prevention Trials as of May 9, 2022

Dynamic Prevention Study	Intervention and Control, (N) Uganda	Intervention (N) Uganda	Intervention and Control, (N) Kenya	Intervention (N) Kenya	Total Enrolled (N), Intervention and Control	Total Enrolled Intervention (N)
Antenatal/SRH Clinic	200	100	201	103	401	203
Outpatient Department Clinics	201	100	201	97	402	197
Household Study Community Village Health Team (VHT)	200	83	210	110	410	193
All Trials Together	601	283	612	310	1213	593

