21.1 Overview

This section provides an overview of the statistical consideration.

The primary study endpoint in this extension will be biomedical covered time defined as the proportion of follow-up time that the participant is protected from HIV infection by any PEP or PrEP (inclusive of CAB-LA). Follow-up will be over the 48 weeks following re-consent for the CAB-LA extension. At risk covered time will be a secondary outcome, defined as the proportion of at-risk follow-up time that the participant is protected from HIV infection by any PEP or PrEP (inclusive of CAB-LA). We will also conduct sensitivity analyses, varying the definitions of coverage and risk. For example, we will also examine covered time from CAB-LA only (i.e., exclusive of oral PrEP or PEP), and we will conduct a sensitivity analysis in which we treat time after loss to follow-up among persons not known to have moved out of the study region and time after study withdrawal as presumed to be non-covered.

For our primary objective in this extension, we will compare covered time during the 48 week CAB-LA extension between the intervention and control arms. For improved efficiency, Targeted Maximum Likelihood Estimation (TMLE) will be used to adjust for differences in baseline participant characteristics between the two trial arms, accounting for the stratified randomization design. In secondary analyses, we will further use TMLE to i) adjust for measured differences between arms at time of start of the CAB-LA extension period; and, ii) adjust for baseline and time-varying factors that are predictive of the outcome and that differ between persons that do vs. do not have their follow-up time censored. The primary analysis will pool over the trials, accounting for clustering inherent in the community trial; secondary analyses will stratify by trial site. We will test the null hypothesis that covered time is the same between arms with a two-sided test at the 5% significance level.

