4.2. Secondary Endpoint Analysis: Effect on At-Risk Coverage

We will implement analogous analyses to assess the SEARCH effect on coverage during periods of self-reported HIV risk. We will use the same approach for effect estimation, statistical inference, and multiple testing. We will conduct analogous subgroup and sensitivity analyses.

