6. SENSITIVITY ANALYSES

In this extension study, participants will maintain their original randomization arm. As a result, there is a legitimate concern that arms will be imbalanced at the start of the extension study. We will address this concern by conducting the following sensitivity analyses for the effect on biomedical HIV prevention coverage (primary endpoint) and at-risk coverage (secondary endpoint). These analyses will incorporate data from all persons who participated in the 3 Dynamic Choice HIV Prevention trials – regardless if they continued in the extension and/or had their endpoint ascertained in the extension.

This sensitivity analysis is informed by the Causal Roadmap¹⁶ and aims to address possible bias due to selection and missing data. Specifically, we can frame the analysis as asking, “What is the effect of the SEARCH Dynamic Choice HIV Prevention intervention (including the option of CAB-LA) if all participants had continued in the extension and had their endpoint ascertained?” While the treatment arm is randomized, we need to make the following missing data assumption: within values of adjustment variables, participants with their endpoint measured in the extension (and, thus, continued in the extension) are representative of participants who do not. Here, our adjustment set includes variables measured at recruitment into the initial trials (hereafter “baseline”): age, sex, country, recruitment site, alcohol use, and mobility. Importantly, our adjustment set also includes trial arm as well as post-intervention variables measured prior to the extension start: biomedical HIV prevention coverage, at-risk coverage, follow-up time, and follow-up time with self-reported risk of HIV acquisition. We additionally need that there is a positive probability of endpoint ascertainment within all possible values of these adjustment variables.

Under these assumptions, our statistical estimand is given by the Longitudinal G-computation formula:¹⁷

$$\mathbb{E}\{\mathbb{E}[\mathbb{E}(Y|\Delta = 1, L1, A = 1, L0)|A = 1, L0]\} - \mathbb{E}\{\mathbb{E}[\mathbb{E}(Y|\Delta = 1, L1, A = 0, L0)|A = 0, L0]\}$$

where Y is the endpoint, Δ is an indicator of having that endpoint measured and, thus, continuing in the extension, $L1$ are the time-varying covariates, A is an indicator of being randomized to the intervention arm, and $L0$ are the baseline covariates.

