7. POWER CALCULATIONS

We assume 70% of participants in the 3 Dynamic Choice HIV Prevention trials enroll in the extension. Of those, we assume 90% have measures of biomedical HIV prevention coverage (the primary endpoint). Then using standard formulas for continuous outcomes with clustering,^{20,21} we anticipate at least 80% power to detect at least a 7.5% absolute increase in prevention coverage with 485 participants/arm, an outcome standard deviation of 0.35, and a design effect of 1.3. As shown in Figure 2, these calculations are fairly robust to alternative assumptions, including lower outcome measurement

and higher design effects. We further expect these calculations to be conservative given the precision gains due to covariate adjustment with TMLE in the primary analysis.

Figure 2: Minimal effect size (difference) detected with 80% power with a two-sample t-test (via `power.t.test` in R) after deflating the sample size by the design effect

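### Country is already collected but cannot enter the primary TMLE; adding it as a candidate needs no new data and may gain some precision

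*SAP*

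**What the plan says.** SAP 4.1 adjusts the primary coverage comparison for recruitment setting. It then lets 10-fold cross-validation pick the most efficient TMLE from a fixed set of models, restricted to these inputs: "Candidate variables: sex, age, alcohol use, mobility, or nothing". SAP 4.2 carries this over to at-risk coverage: "We will use the same approach for effect estimation, statistical inference, and multiple testing".

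Country appears elsewhere in the plan. SAP 2 lists it among the characteristics summarised at the start of the extension ("recruitment setting, country, sex, age, marital status, occupation"). SAP 6 puts it in the baseline adjustment set of the longitudinal TMLE ("age, sex, country, recruitment site, alcohol use, and mobility"), where the adjustment set supports a missing-data assumption.

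Protocol 21.1 says the TMLE will adjust for baseline characteristics, "accounting for the stratified randomization design". The strata are not named in the available text. SAP 4.1 also promises a check before lock: "we will conduct treatment-blind simulations to verify Type-I error control for all endpoints".

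**The concern.** The adaptive step exists to gain precision, and a variable left off the list cannot be chosen however well it predicts the outcome. Country is a natural candidate. Each of the three trials ran in both countries in nearly equal numbers, so setting is no proxy for it. Protocol 7.2 says standard care differs by country, which makes a coverage difference plausible. The SAP gives no reason for leaving it out.

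If coverage does differ by country, two things are lost. The confidence interval is wider than it need be, and any chance imbalance in country between the arms stays in the point estimate. If allocation was in fact stratified by country, imbalance is limited by design. The loss is then mainly an overstated standard error and a conservative test.

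**Working it through.** **1. The plan's own power figure.** SAP 7 gives 485 per arm, SD 0.35, design effect 1.3, two-sided 5%.

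- Effective n per arm = 485 / 1.3 = 373.1.
- Two-sample t-test: power at 0.075 is 83.2%, and the difference detectable with 80% power is 7.19 points. This agrees with the stated minimum of 80%.
- SE of the difference = 0.35 × √(2/373.1) = 0.0256, or 2.6 points.
- If 485 means enrolled and 90% are measured, effective n is 335.8 and power is 79.2%. The gains below are of similar size on that reading.

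**2. What country could add.** Protocol Table 1 ("Enrollment in 3 SEARCH Sapphire Dynamic Prevention Trials as of May 9, 2022") gives a Uganda share p = 601/1213 = 0.495. Let g be the country gap in mean coverage beyond the other covariates. The documents do not give g, so a range is assumed. Then R² = g² p(1−p) / 0.35², and the SE is multiplied by √(1−R²).

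| Assumed gap (points) | R² | SE reduction | Power at 7.5 points | Detectable effect (points) |
|---|---|---|---|---|
| 0 | 0 | 0% | 83.2% | 7.19 |
| 10 | 0.020 | 1.0% | 84.0% | 7.11 |
| 20 | 0.082 | 4.2% | 86.2% | 6.89 |
| 30 | 0.184 | 9.6% | 89.9% | 6.50 |

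**3. Imbalance by country in Table 1.** Control counts are totals minus intervention counts.

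| Trial | Kenya share, intervention | Kenya share, control | Difference (points) |
|---|---|---|---|
| Antenatal | 103/203 = 50.7% | 98/198 = 49.5% | +1.2 |
| Outpatient | 97/197 = 49.2% | 104/205 = 50.7% | −1.5 |
| Community | 110/193 = 57.0% | 100/217 = 46.1% | +10.9 |
| Pooled | 310/593 = 52.3% | 302/620 = 48.7% | +3.6 |

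In the community trial the intervention share is 83/200 = 41.5% in Uganda and 110/210 = 52.4% in Kenya. To adjust for setting, weight each trial's difference by n₁n₀/n (100.2, 100.5 and 102.2). The result is again +3.6, so adjusting for setting does not remove the imbalance.

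The shift in the estimate is gap × imbalance. Gaps of 10, 20 and 30 points move the pooled estimate by 0.4, 0.7 and 1.1 points, and the community-trial estimate by 1.1, 2.2 and 3.3 points.

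**4. Is there a penalty for adding it?** A simplified simulation of the adaptive step was run 2,000 times per case. It used 970 people, 16 community clusters with pairs assumed matched within country, linear models, and no LASSO or propensity-score candidates. Simulation error on Type-I error is about 0.5 points.

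| Gap (points) | Country a candidate? | Type-I error | Power at 7.5 points | Mean estimated SE | Actual SD of estimate |
|---|---|---|---|---|---|
| 0 | no | 5.6% | 88.0% | 0.0233 | 0.0240 |
| 0 | yes | 5.6% | 88.1% | 0.0232 | 0.0240 |
| 10 | no | 4.2% | 84.4% | 0.0248 | 0.0242 |
| 10 | yes | 5.9% | 87.8% | 0.0232 | 0.0241 |
| 20 | no | 2.0% | not run | 0.0289 | 0.0247 |

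With no gap there is no penalty. With a gap, and clusters balanced by country, leaving country out overstates the SE and makes the test conservative. Adding it cuts the estimated SE by 1 − 0.0232/0.0248 = 6.5% at 10 points, more than the 1.0% from the individual-level formula, because country is constant within a cluster. The actual spread of the estimate hardly changes, so in this design the gain comes from correcting the SE. A repeat of the exercise gave SE reductions of about 7% and 22% at 10 and 20 points. The simulated power is not comparable with 83.2%, because clustering in the simulation is milder than an overall design effect of 1.3.

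**The case against.** The best case against runs as follows.

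- **SAP 6 already handles imbalance.** It raises that concern and adjusts for country and recruitment site for both coverage endpoints, and it credits the Super Learner with efficiency as well. This is true, but it is a sensitivity analysis. The primary estimate and its test remain without country.
- **The upper end of the range is unrealistic.** Protocol 21.5 assumes 10% coverage under standard care in the community trial. With a 7.5-point effect the overall mean is 13.75%. With a near-even country split the gap cannot then exceed about 27.5 points, and a 20-point gap needs roughly 4% against 24%. This stands: the 30-point row is implausible unless coverage is higher in the other settings, and the 10-point row deserves the most weight.
- **Table 1 describes parent-trial enrolment.** The extension sample may differ. This also stands, so the shifts are conditional. A shift of 0.4 to 0.7 points is in any case small beside an SE of 2.6 points.
- **Type-I error rose from 4.2% to 5.9% at a 10-point gap.** The 5.9% is close to the 5.6% seen with no gap, with or without country. The slight excess is what 16 clusters with Wald inference would be expected to give, and country does not create it. It is still a reason to repeat the planned simulations with the longer list.
- **A short prespecified list is legitimate.** Marital status and occupation are collected and also left out. This is fair, and it is why the point is optional. Country has the stronger claim because the protocol itself says standard care differs by country.

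**Conclusion.** The point holds as an optional improvement. Country is available, is not represented by setting, and is shut out of the primary and at-risk coverage analyses without a stated reason. The benefit depends on an undocumented country gap. It is zero with no gap, and by the formula about 1% of the SE at 10 points and 4% at 20. It would be more if community clusters are balanced by country, as the simulation assumed.

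No bias, power shortfall or departure from the protocol is shown. Omitting a baseline covariate leaves a randomized comparison valid. SAP 7 treats covariate gains as extra margin ("We further expect these calculations to be conservative given the precision gains due to covariate adjustment with TMLE"), and its power reproduces without them. Whether country was a randomization stratum cannot be settled from the available text.

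**What to change.** In SAP 4.1, add country to the candidate variables, so that it also applies to at-risk coverage through SAP 4.2 and cross-validation may select or decline it. Add one sentence naming the randomization strata of the three trials. Any factor that was an actual stratum, including country if it was one, should be forced into the outcome regression. Include the longer list in the treatment-blind Type-I error simulations, and make the change before SAP lock and unblinding. Keep the setting-only and unadjusted estimators as sensitivity analyses.

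The cost is one word in the list, one sentence on strata, and inclusion of country in simulations already planned. No new data are needed.
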